8.5.2. Key Secondary Efficacy Outcome Measures

Time-to event data will be analysed using the Kaplan-Meier method and presented with 95% CIs. A Cox-regression model, including the levels of the randomisation stratification factors as covariates, will be applied to compare results between each dose of plitidepsin *versus* control arm. Hazard ratios, 2-sided 95% CIs, and p-values for the comparison of each dose of plitidepsin *versus* control arm will be presented.

In the event that the primary endpoint is significant for both doses, the Hochberg procedure will be used to test the key secondary efficacy endpoints at the overall (2-sided) significance level of 0.05. This adjustment will not apply if the accrual in any of the experimental arms is stopped after the interim futility analysis. Details will be provided in the SAP.

8.5.3. Other Secondary Efficacy Outcome Measures

Descriptive statistics for the other secondary efficacy endpoints will be presented by treatment group and by study visit where appropriate. We will use similar methods as specified for the analyses of the primary and secondary variables.

For binary endpoints, the treatment group comparisons will be performed at Day 8 (± 1 day) only, with descriptive statistics provided for each clinic visit.

Longitudinal analyses will be also performed assuming mixed-effect models including treatment effect, time effect, randomisation stratification factor and a time-treatment interaction as covariates, using a covariance structure of autoregressive order 1.

The clinical status, as assessed on the 11-point WHO Clinical Progression Scale ([Appendix 13](#)) on Day 8 (± 1 day), will be summarised by treatment group. The clinical status at Day 8 (± 1 day) between each dose of plitidepsin *versus* control arm will be compared using a proportional odds model. The model will be adjusted for the randomisation stratification factors. The odds ratios, 2-sided 95% CIs, and p-values for the comparison of each dose of plitidepsin *versus* control arm will be presented.

8.6. Subgroup Analyses

The primary and key secondary efficacy endpoints will be analysed by the following subgroups:

- Geographical Region (Europe *versus* Rest of the World).
- Charlson Comorbidity Index: 0-1 *versus* >1 ([Appendix 11 – Age-adjusted Charlson Index](#)).
- Barthel index (≥ 90 *versus* <90) ([Appendix 7 – Barthel Index for Functional Assessment](#)).

Additionally, the primary efficacy endpoint will be analysed by the following subgroups:

- Sex: female or male.
- Age at study entry: 18 to 39, 40 to 64, ≥ 65 years.
- Race: Asian, black, white, or other.

- Ethnic group: Hispanic or Latino or Not Hispanic or Latino.
- Site location: analyses will be performed to assess that no single study site provided an unusually large fraction of the patients and that no single investigator or site was disproportionately responsible for the favourable effect seen.
- User of antiviral therapies or immunomodulatory drugs.
- Previous COVID-19 vaccination status (complete/incomplete/no).
- Anti-SARS-CoV-2 IgG Day 1 (non-positive/positive).
- Pre-randomisation dexamethasone (yes/no).
- Total duration of corticoid therapy (± 10 days).
- Total cumulative dose of corticoid therapy (≤ 60 or >60 mg dexamethasone or equivalent) (See [Appendix 15 – Glucocorticoids equivalent anti-inflammatory doses](#)).
- Days of symptoms (≤ 5 days, 5-10 days, > 10 days).
- Administration of approved antivirals if the patient is randomised to the control arm (remdesivir/favipiravir/no).
- Other exploratory subgroup analyses may be prespecified in the SAP based on prognostic factors of medical interest (e.g., baseline measures of the disease status or laboratory parameters such as, LDH, CRP, D-dimer, ferritin, etc.).
- SARS-CoV-2 variant analysis (United Kingdom α , South Africa β , Brazil γ , India δ , California ϵ , Peru λ , and New York ι) and potential new variants when emerging in the selected countries.⁵¹
- Patients included before and after amendment (protocol v.6 *versus* v.7).

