- Percentage of patients in each study group requiring non-invasive mechanical ventilation on Days 4, 8, 15, and 31.
- Percentage of patients requiring either extracorporeal membrane oxygenation ECMO or invasive mechanical ventilation by Days 4, 8, 15, and 31.
- Time to initiation with immune-modulating drugs.
- Time to initiation with antiviral drugs.
- Percentage of patients receiving subsequent immune-modulating drugs on Days 4, 8, 15 and 31.
- Percentage of patients receiving subsequent antiviral drugs on Days 4, 8, 15 and 31.
- Percentage of patients in each study group with nosocomial infection by Days 4, 8, 15 and 31.
- Mortality in each study group on Days 4, 8, 15 and 31.
- Change in SARS-CoV-2 viral load in each study group from Day 1 before administration of the study drug until Day 8.
- Percentage of patients in each study group with undetectable SARS-CoV-2 viral load on Day 8.
- Change in inflammatory biomarkers (C-reactive protein [CRP], ferritin, interleukin [IL]-6, IL-1 β , IL-10 and tumour necrosis factor alpha [TNF α]) in each study group from baseline until Days 2, 3, 4, 8, and 31.
- Change respect to baseline in individual serological assessments.
- Obesity, hypertension, age and individual co-morbidities included in the Charlson Index ([Appendix 11- Age-adjusted Charlson Index](#)), ISARIC-4C score ([Appendix 14 - ISARIC 4C Mortality & 4C Deterioration Scores](#)), or vaccination status.
- Time to sustained withdrawal of supplementary oxygen (11-category WHO Clinical Progression Scale \leq 4) with no subsequent reutilisation during remaining study period, before (protocol v.6) and after the amendment (protocol v.7).
- Time to sustained (i.e., with no subsequent readmission to Day 31) hospital discharge (since randomisation), before (protocol v.6) and after the amendment (protocol v.7).

Additionally, a dedicated QTc substudy will be performed in a subset of approximately 50 patients with ECGs collected over Days 1 to 3 using Holter monitors to assess treatment impact on QTc prolongation. See [Appendix 8](#) for objectives and respective endpoints planned for the QTc substudy. The substudy patients will have blood sampling for pharmacokinetic assessments over Days 1 to 4.

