15 Treatment-emergent adverse events (TEAEs): TEAEs should be documented and recorded at each visit (i.e., from initiation of study treatment on Day 1 through at least Day 31), grading severity assessed using National Cancer Institute (NCI) Common Terminology for Adverse Events (CTCAE) v5.0, and relationship to study treatment assessed by investigator judgement

16 Concomitant medications: Concomitant medications and treatments will be recorded for all patients from 28 days before the start of study treatment and through study Day 31 (± 3 days). All COVID-19 vaccinations should be recorded, regardless of when they were given, until the end of study.

17 Dexamethasone treatment: On all study arms, patients will receive dexamethasone phosphate 8 mg/day IV (equivalent to 6.6 mg dexamethasone base) on Days 1 to 3 (administered as a premedication in plitidepsin arms), following by dexamethasone phosphate 7.2 mg (equivalent to 6 mg/day dexamethasone base) PO/IV from Day 4 and up to a total cumulative dose of 60 mg of dexamethasone base (as per physician judgement according to patient clinical condition and evolution). The study allows up to a total cumulative dose of 60 mg of dexamethasone base (calculation of the total dose will also include corticosteroids administered within 72 hours before the start of the study treatment and dexamethasone administered as premedication).

18 Plitidepsin treatment: Plitidepsin 1.5 or 2.5 mg intravenous (IV) infusion for 60 minutes will be administered on Days 1 to 3. A 30 (± 5) minute window is allowed for the plitidepsin administration between each day, and plitidepsin should not be given earlier than 23.5 hours on Days 2 and 3 of previous day plitidepsin administration. No other antiviral agents to be administered during Days 1 to 3.

19 Remdesivir treatment: Consistent with local treatment guidelines, patients randomised to the control arm may receive remdesivir 200 mg IV on Day 1 followed by 100 mg/day IV on Days 2 to 5.

20 Favipiravir treatment: Consistent with local treatment guidelines, patients randomised to the control arm may receive favipiravir 1600 mg BID PO on Day 1, followed by 600 mg BID PO daily for 2 to 5 days.

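### Section 8.6 sets three primary-endpoint subgroups by treatment received after randomisation, one of them in the control arm only, so they cannot give valid subgroup treatment effects

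*Protocol*

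**What the plan says.** Section 8.6 first names the three stratification factors as subgroups, then continues: "Additionally, the primary efficacy endpoint will be analysed by the following subgroups". Most items in that second list are baseline characteristics. Three are not:

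- "Total duration of corticoid therapy", with a cut at 10 days (printed as ±10, read here as ≤10 versus >10);
- "Total cumulative dose of corticoid therapy", cut at 60 mg dexamethasone or equivalent;
- "Administration of approved antivirals if the patient is randomised to the control arm (remdesivir/favipiravir/no").

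The same list has a separate item, "Pre-randomisation dexamethasone (yes/no"), so the two corticoid totals are evidently not meant as baseline factors. A further item, "User of antiviral therapies or immunomodulatory drugs", carries no time window.

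Other sections show how these exposures arise. Under section 5.1, dexamethasone from Day 4 is left to physician judgement of the patient's condition and evolution, up to 60 mg cumulative base. Section 6.1.1 lets dose and duration be adjusted on clinical deterioration. The notes to Figure 1 and section 8.1 count steroids from the preceding 72 hours and premedication towards the 60 mg. Section 7.4.2 makes remdesivir or favipiravir a physician decision for patients already randomised to control. For the plitidepsin arms, the plitidepsin note in Appendix 5 states: "No other antiviral agents to be administered during Days 1 to 3". Section 3.1 describes the trial as open-label.

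**The concern.** A subgroup treatment effect keeps the protection of randomisation only if membership is settled before allocation, or at least cannot be influenced by treatment or outcome. The two corticoid totals depend on how quickly the patient recovers, and recovery is the endpoint. If plitidepsin shortens time on oxygen, it also changes who falls into the short-course and long-course groups, and the arms are no longer comparable within either.

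The antiviral item fails more basically. It is defined only for control patients, so its remdesivir and favipiravir levels contain no plitidepsin patients. The only contrast available sets physician-selected controls against all plitidepsin patients, or against some other non-randomised set.

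At stake is the reading of the trial, not its primary test. Control is dexamethasone with or without an antiviral, so how plitidepsin compares with an antiviral-treated control is an obvious question. This subgroup is the listed analysis that addresses it directly, and it cannot answer it. Section 8.7 uses the same control-arm factor for safety subgroups.

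**Working it through.** **Inputs from the protocol.** Control median 8 days, target hazard ratio (HR) 1.4 and plitidepsin median 5.7 days (section 8.1); dexamethasone base 6.6 mg/day on Days 1 to 3, then 6 mg/day, with a 60 mg cumulative limit (section 5.1); 203 patients per arm; follow-up to Day 31.

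**Check of the planning figures.** Under exponential times, 8 / 1.4 = 5.7 days, as stated. The point itself rests on no figure in the plan.

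**Where the corticoid cuts fall.** Days 1 to 3 give 3 × 6.6 = 19.8 mg. The remaining 60 − 19.8 = 40.2 mg at 6 mg/day lasts 6.7 days, so the limit is reached at 3 + 6.7 = 9.7 treatment days. The 10-day and 60 mg cuts therefore sit almost on the planned maximum. Apart from use outside the schedule, exceeding 60 mg points to adjustment for deterioration. Steroid given in the 72 hours before treatment brings the limit forward.

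**Corticoid duration.** Simulation of 1.5 million patients, exponential time on oxygen T, true HR 1.4 in everyone. The link between T and steroid duration is an assumption, so a range is shown. In the capped rows, courses stop at 9.7 days except in a stated share of patients still on oxygen after Day 8.

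| Assumed steroid duration | Share ≤10 days | HR, ≤10 days |
|---|---|---|
| T + Normal(0, SD 2), no cap | 63% | about 1.10 |
| 0.5T + 5 + Normal(0, SD 4), no cap | 56% | about 1.16 |
| Capped; 10% run longer | 96% | 1.39 |
| Capped; 20% run longer | 91% | 1.38 |
| Capped; 30% run longer | 87% | 1.37 |

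In the two uncapped rows the >10-day HRs are about 1.40 and 1.47. With a true HR of 1.0 and the same steroid rule in both arms, every setting gives about 1.00 in both strata.

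**Control-only antiviral item.** Plitidepsin patients in the remdesivir and favipiravir levels: 0 by definition, so no within-level HR can be estimated. To illustrate the available contrast, each control level was compared with all plitidepsin patients (203 per arm, 1000 simulated trials per setting). The assumptions are no true effect, log-hazard prognosis with SD 0.3 to 1.0, and sicker controls more likely to receive an antiviral.

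| Prognosis SD | HR against antiviral users (rejections at nominal 5%) | HR against non-users (rejections at nominal 5%) |
|---|---|---|
| 0.3 | 1.12 (15%) | 0.88 (17%) |
| 0.7 | 1.24 (36%) | 0.78 (47%) |
| 1.0 | 1.32 (51%) | 0.74 (65%) |

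If healthier controls were the ones treated, the directions would reverse. The sign and size depend on prescribing habits, which the comparison cannot separate from treatment.

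**The case against.** The strongest reply is that little rests on these analyses. They carry no alpha and no decision rule, section 8.6 itself speaks of further exploratory subgroups, and a statistical analysis plan could label them descriptive. That stands as a limit on consequence. It does not rescue the definitions, because the protocol commits to analysing the primary endpoint by these factors, and a label does not supply plitidepsin patients to the control-only levels.

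A second reply is that the planned steroid limit leaves little room for distortion. This also stands. A reader might infer from the uncapped results that most patients, those on short courses, would appear to gain almost nothing. The documents do not support that: it requires steroid courses that ignore the 60 mg limit. Nor will the corticoid subgroups mislead in every case, since there is no distortion without a treatment effect when practice is the same in all arms.

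Two further readings go too far:

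- "User of antiviral therapies or immunomodulatory drugs" need not mean on-study use. Exclusion criterion 5 in section 4.2 allows certain earlier antivirals, so a baseline reading is possible. The item is ambiguous, not wrong.
- From "Time to initiation with antiviral drugs" (section 2.2) and the Days 1 to 3 antiviral restriction in Appendix 5, a reader might infer that control patients accrue endpoint events simply by starting their permitted antiviral. Sections 5.1 and 8.4 treat those antivirals as study treatment, and the synopsis places the endpoint under intensification of therapy. Nothing says the permitted course counts as an event.

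**Conclusion.** The point holds for three items: total corticoid duration, total cumulative corticoid dose and control-arm antiviral use. None can be read as a randomised subgroup comparison. For the antiviral item this follows from its definition and needs no modelling. For corticoid duration the size is uncertain: against a true HR of 1.4, the ≤10-day subgroup shows about 1.10 to 1.16 if duration follows oxygen use uncapped, and about 1.37 to 1.39 if the 60 mg limit mostly holds. Those ranges rest on exponential times and an assumed link between steroid and oxygen duration. The dose cut was not simulated separately; it sits at nearly the same place on the planned schedule and shares the same mechanism. The primary intent-to-treat test, the multiplicity procedure, alpha and sample size are untouched. This is a correction to supportive analyses, worth making because it is cheap and because the antiviral background bears on interpretation.

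**What to change.** - Remove the three items from the subgroup treatment-effect analyses in section 8.6 and tabulate them descriptively by arm. Treat the control-arm antiviral factor in section 8.7 in the same way.
- Keep pre-randomisation dexamethasone as a subgroup.
- Restrict the antiviral or immunomodulator user item to use before randomisation.
- To examine the antiviral background, use a factor definable before allocation in all three arms, such as country or site antiviral practice. A field in the randomisation system recording the antiviral intended if the patient is allocated to control is an optional addition for patients not yet randomised.

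The cost is wording in the protocol or analysis plan, with no change to treatment or to the primary analysis. The limitation is that country or site practice is a weak proxy, because the choice is made physician by physician. An intended-antiviral field would be more direct, but it would have to be rolled out across about 103 sites and could not cover patients already enrolled.

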8.7. Safety Analysis

Safety analyses will be based on the As Treated Population. All safety parameters will be summarised and also listed by patient.

Treatment-emergent Adverse Events: The verbatim terms used in the eCRF by investigators to identify TEAEs will be coded using the Medical Dictionary for Regulatory Activities (MedDRA) and will be graded according to NCI CTCAE version 5.0. All reported AEs that occur or worsen on or after the first dose of study drug (Day 1) up through Day 31 (± 3 days) (last protocol-specified follow-up visit) will be included in the analysis. Treatment-emergent AEs will be summarised by MedDRA system organ class and preferred term. For each TEAE, the percentage of subjects who experience at least 1 occurrence of the TEAE will be summarised overall and by treatment group. The SAEs, AEs of special interest, and deaths will be listed. All TEAEs resulting in discontinuation of study treatment, dose modification, dose interruption, or a delay in treatment with the study drug will be listed and summarised by system organ class/preferred term.

Clinical Laboratory Tests: Laboratory data will be summarised by type of laboratory test. The worst toxicity grade will be tabulated. Parameters with predefined NCI CTCAE version 5.0 toxicity grades will be summarised. Change from baseline to the worst TEAE grade experienced by the subject during the study will be provided as shift tables.

Electrocardiograms: The effects of treatment on QTcF interval, including events of QTcF >500 msec and >60 msec from baseline, will be evaluated by means of descriptive statistics and frequency tabulations.

Subgroup analysis of TEAEs and clinically relevant laboratory tests will be performed based on prognostic factors of medical interest (e.g., sex, age, administration of remdesivir/favipiravir in the control arm, etc.).

8.8. Pharmacokinetic Analysis

Only applicable for [Appendix 8 \(Protocol for QTc Substudy\)](#).

8.9. Futility Analysis

A futility analysis for efficacy/safety will be performed when 33% of events (sustained withdrawal of supplementary oxygen) have been reached. The rho family of beta-spending functions (with $\rho=1.18$) will be used for the calculation of the stopping boundaries for futility in order to control type II error. The stopping boundaries for the futility analysis will be calculated with the actual number of events available in the ITT population at that moment; if the number of events at the futility analysis is 116 in a pair comparison patients, the beta-spending p-value to reject the alternative hypothesis should be higher or equal than 0.4993 and this p-value is associated with a $HR \leq 1.0382$.

If the recommendation of the IDMC is to discontinue one of the plitidepsin dosing arms at this futility analysis following the stopping rules, the study will continue from that point on a 1:1 randomisation fashion until the completion of the remaining treatment arms (203 patients per arm and 353 events of sustained withdrawal of supplementary oxygen in total necessary to perform the final analysis). The patients still ongoing in the dropped arm would continue to be followed up as per protocol and a Bonferroni-adjusted type I error rate of 1.25% will be kept for the comparison of the primary endpoint between the remaining plitidepsin arm and the control arm.

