4.5. Stopping Rules

The study will consist of approximately 609 patients included in the ITT population and randomised as 1:1:1 to 3 arms (plitidepsin 1.5 mg, plitidepsin 2.5 mg, and control) with 203 patients in each arm. A futility analysis for efficacy/safety will be performed when 33% of events (sustained withdrawal of supplementary oxygen) have been reached. The rho family of beta-spending functions (with $\rho=1.18$) will be used for the calculation of the stopping boundaries for futility in order to control type II error. The stopping boundaries for the futility analysis will be calculated with the actual number of events available in the ITT population at that moment; if the number of events at the futility analysis is 116 in a pair comparison, the beta-spending corrected p-value to reject the alternative hypothesis should be higher or equal than 0.4199 and this p-value is associated with a $HR \leq 1.0382$.

If the recommendation of the IDMC is to discontinue one of the plitidepsin dosing arms at this futility analysis following the stopping rules, the study will continue from that point on a 1:1 randomisation fashion until the completion of the remaining treatment arms (203 patients per arm and 353 events of sustained withdrawal of supplementary oxygen in total necessary to perform the final analysis). The patients still ongoing in the dropped arm would continue to be followed up as per protocol.

Study Termination

The sponsor reserves the right to close a study site or terminate the study at any time for any reason at the sole discretion of the sponsor. Study sites will be closed upon study completion. A study site is considered closed when all required documents and study supplies have been collected and a study site closure visit has been performed. Reasons for study termination may include, but are not limited to:

- Adverse events unknown to date (i.e., not previously reported in any similar investigational study drug trial with respect to their nature, severity, and/or duration).
- Increased frequency and/or severity and/or duration of known, anticipated, or previously reported AEs (this may also apply to AEs defined at enrolment as baseline signs and symptoms).
- Medical or ethical reasons affecting the continued performance of the study.
- Difficulties in the recruitment of patients.
- Cancellation of drug development.

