A total sample size of 609 patients (203 in each arm) with 530 events necessary for the analysis of the primary endpoint has been calculated based on assumptions of a 1-sided type I error of 1.25% ($\alpha=0.0125$) with at least 80% power ($\beta=0.2$) to detect target hazard ratio (HR) of 1.4 in the time to sustained withdrawal of supplementary oxygen, which means a decrease in the median time to the event from 8 days⁴⁸ (control arm) to 5.7 days (plitidepsin). This sample size is adjusted for the multiple comparisons of each plitidepsin arm with control group by a Bonferroni adjustment. At the final analysis, if the HR is 1.27 or greater, in favour of any plitidepsin arm (equivalent to a decrease in the median time to sustained withdrawal of supplementary oxygen of 1.7 days or greater), then it is expected that the null hypothesis (i.e., $HR \leq 1$) will be rejected.

A futility analysis for efficacy/safety will be performed when 33% of events (sustained withdrawal of supplementary oxygen) have been reached. The rho family of beta-spending functions ($\rho=1.18$) will be used for the calculation of the stopping boundaries for futility in order to control type II error. The stopping boundaries for the futility analysis will be calculated with the actual number of events available in the ITT population at that moment; if the number of

events at the futility analysis is 116 in a pair comparison, the beta-spending corrected p-value to reject the alternative hypothesis should be higher or equal than 0.4199 and this p-value is associated with a $HR \leq 1.0382$.

If the recommendation of the IDMC is to discontinue one of the plitidepsin dosing arms at this futility analysis following the stopping rules, the study will continue from that point on a 1:1 randomisation fashion until the completion of the remaining treatment arms (203 patients per arm and 353 events of sustained withdrawal of supplementary oxygen in total necessary to perform the final analysis). The patients still ongoing in the dropped arm would continue to be followed up as per protocol.

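### Section 8.9 sets the futility p-value at 0.4993; the protocol's own hazard ratio, event count and spending function all give 0.4199, as four other sections state

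*Protocol*

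**What the plan says.** Section 8.9 of the protocol is the section devoted to the futility analysis. The look is to be "performed when 33% of events" have occurred, and "The rho family of beta-spending functions (with $\rho=1.18$) will be used" to set the boundary. A worked case with 116 pairwise events follows, and its rule reads "the beta-spending p-value to reject the alternative hypothesis should be higher or equal than 0.4993 and this p-value is associated with a" stated bound on the HR, namely 1.0382.

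Section 4.5 (Stopping Rules) covers the same case with the same rho, event count and HR, but says "the beta-spending corrected p-value to reject the alternative hypothesis should be higher or equal than 0.4199". The synopsis (number of patients), Section 3.1.1 (IDMC) and Section 8.1 (sample size) also give 0.4199. The synopsis paragraph on statistical methods and Section 8.5.1 mention the futility analysis without stating a threshold.

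The design inputs are in Section 8.1: a "1-sided type I error of 1.25" per cent, "with at least 80% power", and a target HR of 1.4. HR above 1 favours plitidepsin. The final analysis needs 530 events over three arms, and Section 8.9 puts the requirement for one pair at 353.

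**The concern.** Five places describe one boundary, and one of them gives a different p-value. Section 8.9 has no different look, event count, rho or HR that could make it a second scenario. It omits the word 'corrected' before the p-value, but that cannot explain the gap, because it ties its p-value to the same HR at the same number of events.

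The boundary governs whether the IDMC recommends dropping a plitidepsin dose. Dropping one changes randomisation to 1:1 and fixes the remaining comparison at the 1.25% level. If two thresholds can be read from the protocol of an open-label trial, the choice between them could be disputed after the interim data have been seen. Section 8.9 is also where a statistician supporting the IDMC would look first.

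**Working it through.** **Inputs.** Events at the look: 116 per pair (8.9). Final events per pair: 353 (8.9), which agrees with 530 × 2/3 = 353.3. Planned look: 0.33 × 353 = 116.5, so 116 is the planned case. Rho = 1.18 (8.9). One-sided alpha = 0.0125, beta = 0.20, target HR = 1.4 (8.1). Allocation within a pair is 1:1.

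**Step 1: HR to p-value.** With equal allocation, z = ln(HR) × √(events/4), and √(116/4) = √29 = 5.385.
- HR 1.0382: z = 0.0375 × 5.385 = 0.202, one-sided p = 0.4200. With 115 or 117 events, p is 0.4203 or 0.4197.

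**Step 2: p-value to HR**, using HR = exp(z/5.385).
- p = 0.4199: z = 0.2021, HR = 1.0383. This agrees with the stated 1.0382 to within rounding.
- p = 0.4993: z = 0.00175, HR = 1.0003.

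A one-sided p this close to 0.5 means an HR of almost exactly 1 at any realistic event count. Reading 0.4993 as two-sided gives HR 1.134. Neither reading gives 1.0382.

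**Step 3: boundary from the spending function.**
- Beta spent at the look: 0.20 × (116/353)^1.18 = 0.0538.
- Simple version, with the drift taken directly from HR 1.4: z = ln(1.4) × 5.385 + Φ⁻¹(0.0538) = 1.812 − 1.609 = 0.203, p = 0.4196.
- Full two-look version: solve for the drift that makes total type II error 0.20, with a non-binding futility bound and a final critical value of 2.2414 (one-sided 0.0125). The drift is 3.160, so the events needed are 4 × (3.160/ln 1.4)² = 352.8, against 353 stated. The look-1 bound is z = 0.2022, p = 0.4199, HR = 1.0383.

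The full version reproduces the planned events, the p-value in the other four sections and, to within rounding, the HR. The final critical HR, exp(2.2414 × 2/√353) = 1.269, also matches the stated 1.27.

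**Step 4: effect of each threshold.** The chance of crossing the futility bound is Φ(z_bound − ln(HR) × 5.385), with z_bound = 0.2021 for 0.4199 and 0.00175 for 0.4993.

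| True HR | Stop at p ≥ 0.4199 | Stop at p ≥ 0.4993 | Difference (points) |
|---|---|---|---|
| 1.0 | 58.0% | 50.1% | 7.9 |
| 1.2 | 21.8% | 16.4% | 5.4 |
| 1.4 | 5.4% | 3.5% | 1.9 |

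The last column is also the chance that the observed result falls where the two thresholds disagree. At HR 1.4, the 0.4199 cut spends the 5.4% that rho = 1.18 prescribes. The 0.4993 cut spends 3.5%, which does not match that function.

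**The case against.** The strongest reply is that 0.4993 is an illustration and not the operative rule. All five places say the boundary will be recomputed from the events actually observed, so a statistician applying rho = 1.18 would obtain the right value whatever 8.9 prints. The intended value can also be recovered from the document: the HR in 8.9 is correct, 8.9 refers to the stopping rules, and Section 4.5 under that title gives 0.4199. Finally, the error makes stopping harder. It cannot inflate type I error, since there is no early stop for efficacy, and it spends less type II error at the look. The cost is a somewhat greater chance of continuing an ineffective arm.

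Most of this stands, and it limits the practical harm. It does not make 0.4993 right. Because 116 is the planned look, the worked example is also the expected case and the benchmark against which a recalculated boundary would be checked. A reader who has only Section 8.9 has a p-value and an HR that give opposite decisions over a range of results, with nothing in that section to say which governs.

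The simple calculation in Step 3 gives 0.4196. The match to 0.4199 relies on a non-binding bound, which the protocol does not state. The direct conversion in Steps 1 and 2 does not need that assumption and is enough to exclude 0.4993.

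**Conclusion.** The p-value of 0.4993 in Section 8.9 is wrong as written. It contradicts the HR in the same sentence and the figure in four other places, and it does not follow from the stated spending function. The HR of 1.0382 in 8.9 is correct, so the error is confined to one number.

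For an observed HR between about 1.0003 and 1.0382 at 116 events, the text gives conflicting decisions. The probability of landing there is about 8% if the true HR is 1.0, 5% at 1.2 and 2% at 1.4.

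These results assume the usual log-rank variance (events/4) with equal allocation in the pair. The full reconstruction also assumes a non-binding futility bound, which is supported by its reproducing both 353 events and 0.4199. Whether the IDMC charter carries the wrong figure cannot be judged, as the charter is not available.

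**What to change.** In Section 8.9, replace 0.4993 with 0.4199 and restore the wording used for this boundary in the other four sections. State in all five places that the p-value is one-sided. Section 8.5.1 specifies a two-sided log-rank test for the primary comparison, and 0.4199 read as two-sided would correspond to HR 1.162. Confirm that the IDMC charter, and the SAP if it repeats the boundary, carry 0.4199 one-sided at 116 events together with the instruction to recalculate from the actual events.

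The cost is one corrected number, a label and a document check, to be done before the futility look. Sample size, event targets and analyses are unchanged.
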